SCTR Nexus clinic at MUSC will be used for study visits 1 and 2, to obtain vital signs, blood and urine collection. Subjects will be asked to avoid consumption of food, drink or caffeine, except water, for 12 hours prior to lab collection and avoid alcohol and exercise for 2 days before lab collection. Fasting blood samples (drawn after 12 hours of fasting in both groups to help match fasting duration), 24 hour urine collection, and food frequency (FFQ), power of food, food cravings, hunger and satiety, sleep and exercise questionnaires will be obtained before start of and at end of intervention. Subjects will be instructed to bring completed 24 hour urine collection to Visit 1 and Visit 2.

Patients will be provided remuneration for participation for each of the two visits and given food voucher after fasting lab draws.

Subjects in both groups will also fill out 2 week sleep diaries during 2 week run in period and last 2 weeks of intervention.

Subjects in both groups will have virtual visits with our psychologist or dietitian, through phone call or established doxy.me platform, at defined intervals throughout the study: pre-intervention, weekly for first month, alternate weeks for second month and once during last month of study. Our psychologist or dietitian will use data on patient self-report to enhance compliance with study group recommendations by use of motivational interviewing strategies. The study coordinator will make phone calls to subjects as needed to encourage compliance.

Blood and urine analysis: Plasma AGE and sRAGE (includes the cRAGE and esRAGE isoforms) will be measured by ELISA (as described in SA2). The Glasgow Prognostic Scoring System is a cumulative inflammation-based cancer-prognostic marker consisting of an assessment of serum elevation of CRP and decrease in albumin concentration by ELISA.

Samples for comprehensive metabolic panel, IGF-1, lipid panel, fasting insulin, uric acid, hemoglobin A1C, C-reactive protein and Apolipoprotein B will be obtained at baseline and at end of study (visit 1 and visit 2).

24-hour urinary AGE will be measured by fluorescence assay.

Urine creatinine will be assessed.

To assess renal handling and clearance, eGFR will be used to calculate AGE fractional excretion, and renal clearance of AGE will be calculated.

Dietary AGE analysis: Daily dietary AGE content from food frequency questionnaires will be estimated using methods we have published previously (30).

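### AGE fractional excretion is to be calculated from eGFR, which keeps 24-hour collection error that the creatinine ratio would cancel at no extra cost

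*Combined protocol and SAP*

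**What the plan says.** The laboratory methods in section 10.0 (Blood and urine analysis) state that, to study how the kidney handles AGE, "eGFR will be used to calculate AGE fractional excretion"; the same sentence adds that renal clearance of AGE is to be computed. No formula, eGFR equation or collection-completeness check is given.

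The same section provides nearly everything needed for the alternative:

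- Timed urine at both visits: "Subjects will be instructed to bring completed 24 hour urine collection to Visit 1 and Visit 2".
- Urine creatinine, with no stated purpose: "Urine creatinine will be assessed".
- Blood chemistry: "Samples for comprehensive metabolic panel, IGF-1, lipid panel, fasting insulin, uric acid, hemoglobin A1C, C-reactive protein and Apolipoprotein B will be obtained at baseline", and again at the end of the study. Serum creatinine is not named, but the metabolic panel and the use of eGFR both imply it.
- Two different AGE assays: "Plasma AGE and sRAGE (includes the cRAGE and esRAGE isoforms) will be measured by ELISA", whereas "24-hour urinary AGE will be measured by fluorescence assay".

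Elsewhere, section 1.0 names renal clearance of AGE among the quantities to be evaluated. Section 4.0 lists 24-hour urinary AGE as a secondary endpoint. Fractional excretion is not listed in section 4.0 and does not appear in the statistical text of section 12.0.

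**The concern.** Fractional excretion is the clearance of a substance divided by the glomerular filtration rate. If the filtration rate comes from eGFR, the numerator has to be an absolute clearance, which depends on the volume collected and the collection time. Anything the participant misses, or adds by collecting too long, passes in full into the answer. A shortfall that repeats exactly at both visits drops out of the relative change. One that differs between visits does not.

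If the filtration rate comes instead from creatinine in the same urine and the same visit's blood, volume, time and completeness appear in both numerator and denominator and cancel.

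The cost is avoidable variance in a small trial. With 22 randomised per arm and the planned 10% attrition, 22 x 0.9 = 19.8, or about 20 per arm, are expected to contribute. Section 12.0 gives the main purpose as estimating effect sizes and variances for a later trial, and a variance inflated by collection error would feed into that planning.

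**Working it through.** The plan prints no figure on this point, so there is none to reproduce. The check is algebra followed by a sensitivity range. All numerical inputs below are assumptions; the documents supply none.

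**Step 1. The two forms.** Let c be the fraction of the true 24-hour urine actually collected, with the missed urine having the same composition as the rest.

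- eGFR form: FE = (urine AGE x volume / time) / (plasma AGE x eGFR)
- Creatinine ratio: FE = (urine AGE x serum creatinine) / (plasma AGE x urine creatinine)

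The eGFR form is the natural reading of the sentence in section 10.0, not its text.

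**Step 2. One example.** Assume true FE 0.10, GFR 90 mL/min, plasma AGE 1 unit/mL, serum creatinine 0.008 mg/mL, true urine volume 1500 mL and c = 0.8.

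- True AGE excretion: 0.10 x 90 x 1 = 9 units/min, or 9 x 1440 = 12,960 units/day.
- True creatinine excretion: 0.008 x 90 x 1440 = 1036.8 mg/day.
- Collected: volume 1200 mL, AGE 10,368 units, creatinine 829.44 mg.
- Concentrations: AGE 10,368 / 1200 = 8.64 units/mL; creatinine 829.44 / 1200 = 0.6912 mg/mL.
- eGFR form: (10,368 / 1440) / (1 x 90) = 7.2 / 90 = 0.080, which is 20% too low.
- Creatinine ratio: (8.64 x 0.008) / (1 x 0.6912) = 0.100, which is correct.

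At c = 1.2 the eGFR form gives 0.120 (20% too high) and the ratio again gives 0.100.

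**Step 3. Creatinine generation.** Let g be relative creatinine generation and let eGFR vary as serum creatinine to the power -b. The eGFR form then becomes 0.10 x c x g^b. With c = 1 and b = 1, g = 0.9 gives 0.090 and g = 1.1 gives 0.110. In the ratio g cancels, provided creatinine is at steady state. A stable personal level of g also cancels in the within-person relative change under the eGFR form, so only a change in g between visits matters there.

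**Step 4. Effect on intervals for the log change.** Completeness with per-visit coefficient of variation CV, independent between visits, adds 2 x ln(1 + CV²) to the variance of the change. Let s be the SD of all other variation in the log change.

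- CV 15%: 2 x ln(1.0225) = 0.0445
- CV 30%: 2 x ln(1.09) = 0.1724

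Variance ratio = (s² + added variance) / s². The interval widens by its square root.

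| s | s² | Variance ratio, CV 15% | Interval widening | Variance ratio, CV 30% | Interval widening |
|---|---|---|---|---|---|
| 0.3 | 0.09 | 1.49 | 22% | 2.92 | 71% |
| 0.4 | 0.16 | 1.28 | 13% | 2.08 | 44% |
| 0.6 | 0.36 | 1.12 | 6% | 1.48 | 22% |
| 0.8 | 0.64 | 1.07 | 3% | 1.27 | 13% |

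Assay noise in plasma and urinary AGE is common to both forms and belongs in s, which argues for looking at the larger values as well as 0.4.

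**Step 5. Body-surface indexing.** Section 5.0 expresses eGFR per 1.73 m². If it is not de-indexed, the level of FE is off by 1.9 / 1.73 = 1.10 at 1.9 m² and 2.1 / 1.73 = 1.21 at 2.1 m² (assumed areas). A person's surface area changes little over 12 weeks, so this largely cancels in relative change.

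**The case against.** The strongest reply is that the quantity is peripheral. Fractional excretion is in neither endpoint list. The listed urinary endpoint and the clearance named in the Specific Aim both rest on the same timed collection, and changing the fractional-excretion formula improves neither. That stands, and it limits the weight of the point.

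The criticised formula is also inferred, and the unexplained urine creatinine may already be meant for a completeness check or for normalisation. That is possible, but the plan does not say so. It does name eGFR as the basis for fractional excretion.

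The size depends wholly on assumed values, and the calculation charges the ratio nothing for measurement error in urine creatinine. Both are fair, and Step 4 therefore shows a range.

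Three stronger readings are tempting, and the documents do not support them:

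- *That eGFR biases the comparison between arms.* This needs serum creatinine to move in one arm through changed muscle mass or meat intake. Section 10.0 gives neither arm any instruction to change diet quality, quantity, calories or activity, and blood is drawn after the same 12-hour fast in both. A shift remains possible, but nothing in the documents gives it a size.
- *That body-surface indexing puts a 10% to 21% error on the treatment effect.* Those figures concern the absolute level far more than the change, and the plan does not say whether eGFR will be de-indexed.
- *That the creatinine ratio yields a true fraction.* It assumes creatinine steady state, pairs a single fasting serum value with 24 hours of urine, and leaves tubular secretion of creatinine in place. With plasma AGE by ELISA and urinary AGE by fluorescence, neither form is a true fraction unless the assays are put on one scale.

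**Conclusion.** The point holds as a modest gain in precision for a supportive, unlisted measure. The plan names a basis for fractional excretion that retains collection error, while the inputs for a form that cancels it are measured (urine creatinine) or implied (serum creatinine) at both visits. The cancellation follows from the algebra; its practical size does not. With a per-visit completeness CV of 15% to 30%, independent between visits, intervals for the log change are about 13% to 44% wider under eGFR if the other variation has SD 0.4, and about 3% to 13% wider if it has SD 0.8. A smaller SD would make the loss larger. No conclusion about bias between arms follows, and the primary endpoints are unaffected.

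**What to change.** In section 10.0, replace the clause on fractional excretion with wording such as: *AGE fractional excretion will be calculated as (urine AGE x serum creatinine) / (plasma AGE x urine creatinine) from samples of the same visit, and reported as a relative index unless the plasma and urine AGE assays are placed on a common scale.* Name serum creatinine explicitly as a measured item. Keep the eGFR version, if wanted, as a sensitivity analysis, and state the eGFR equation and whether it is de-indexed.

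Add one sentence on how urine creatinine will be used to judge completeness of each 24-hour collection. The new formula leaves collection error in 24-hour urinary AGE and in absolute renal clearance, so the completeness check is what helps those two.

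The cost is a change of text only: no new sample, visit or assay, provided that serum creatinine is reported with the metabolic panel, as the planned eGFR already requires.

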11.0 Specimen Collection and Banking

Fasting blood samples (drawn after 12 hours of fasting in both groups to help match fasting duration), 24 hour urine collection, will be obtained before start of and at end of intervention.

All samples will be coded, samples will have results associated with coded label.

The samples will be stored in Hollings Cancer Center Translational Science Laboratory. Associated data will be stored on Division of Endocrinology, Diabetes and Metabolic Diseases MUSC drive and the Department of Public Health Sciences MUSC Server.

The specimens will be stored for a minimum of 2 years (the duration of the study) and or/until the samples are depleted on use for analysis.

[name] will have access to the specimens and associated data including data from analysis.

The research coordinator will transport research specimens from SCTR nexus clinic, using a sealed container containing biohazard label. The samples will be carried in person to the Hollings Cancer Center Translational Science Laboratory for processing and storage in -80° C freezer.

All specimens are for use by [name], his direct collaborators at MUSC and collaborators at Virginia Commonwealth University. Only [name] will have the authority to release samples for analysis. All samples will be coded. We will use a Materials Transfer Agreement to send samples to collaborators at Virginia Commonwealth University. The samples sent to Virginia Commonwealth University will be de-identified.

No samples will be used for genetic analysis. No samples will be saved from the prescreening point of care testing.

Exploratory Analyses: The objective of these exploratory analyses is to determine trends toward statistical significance rather than confirm/refute hypotheses with adequate statistical certainty (power). Descriptive statistics and frequency distributions will be calculated as appropriate for all demographic and baseline clinical variables for the total sample and by intervention and control groups. Data will be transformed, or semi-parametric or nonparametric analysis procedures will be used as needed. Baseline values for variables will be compared for imbalance between intervention and control group using one-way analysis of variance (or nonparametric Kruskal-Wallis one-way ANOVA) followed by a pairwise multiple comparison procedure (e.g. Tukey's procedure), if indicated.

Categorical baseline variables will be compared using chi-square analyses.

The primary analyses will use the intent-to-treat (ITT) sample, comprised of all randomized participants. The completer sample will comprise subjects who complete the 3-month follow-up. Analyses will be carried out separately for the ITT sample and for the completer sample. Missing data for this study arising from premature exits (dropouts) will result if a patient's participation is terminated before the 3 months study period is completed. Participants will not be discontinued from the study because of non-adherence; all will remain in the study unless consent is withdrawn or there are concerns regarding patient safety. We will adopt several approaches to dealing with missing data for the ITT analysis set: for continuous outcomes requiring a single endpoint end-of-study value (change from baseline to 3 months), we will use multiple imputation methods to impute missing 3-month values. We will evaluate the sensitivity of study conclusions to the presence of missing data by comparing the results of ITT to the completer analyses and the imputation results. We will use information on premature exits/missed appointments, food photography and dietary logs as indicators of participation, feasibility and fidelity of the treatment modalities being compared. Because this is a feasibility study, no adjustment will be made for analyses using the primary or secondary outcome measures.

Data Security:

Data confidentiality, Data Acquisition and Management

We plan to use REDCap for data capture and management. REDCap (Research Electronic Data Capture) is a software toolset and workflow methodology for electronic collection and management of research and clinical trial data. REDCap provides secure, web-based flexible applications, including real time validation rules with automated data type and range checks at the time of entry. Exports are made available for several statistical packages including SPSS, SAS, SATA, R and Microsoft Excel.

The study recruitment report, will be housed separately from the data capture in REDCap. Study staff will not have access to the recruitment report after recruitment is complete.

Surveys:

The system allows the research team to create and design online surveys and engage respondents using a variety of notification methods.

Security, Privacy, and Confidentiality

The underlying REDCap database is hosted in a secure data center at MUSC, a secure environment for data systems and servers on campus, and includes redundancy, failover capability, backups and extensive security checks. The system has several layers of protection including, user/group account management, "Data Access Groups" which allow data to be entered by multiple groups in one database with segmented user rights for entered data, audit trails for all changes, queries and reports, and Secure Sockets Layer (SSL) encryption.

The data center in which the REDcap servers are housed has strict access control; only authorized core personnel may access the facility un escorted. Only authorized users are allowed to connect to the network, and the security of the network is actively monitored. Power and environmental controls have several layers of backups, from interruptible power supplies to alternate and redundant feeds to the local utility company. The REDcap system administrator contributes to the maintenance of institutional disaster recovery and business continuity plans. Load balancers and a highly fault tolerant SAN infrastructure contribute to high availability. All transactions are securely delivered to the application using SSL (SHA-1 with RSA Encryption; 2048-bits). It is then transmitted internally (behind the firewall) to the database server. All transactions are logged at the server layer (http logging), application layer (REDCap logs activity to a database table), and the database layer (using both query and binary logging).

The REDcap system relies upon the institution's identity and access management infrastructure. Password complexity, history and expiration standards are implemented at the institutional level. Access to the data is managed by institutionally sponsored login IDs. All personnel must pass an employment background check before being issued an ID. Access to individual REDCap projects (and their data) is managed by the owner of the project.

The physical security of the data center is actively monitored 24x7 by security personnel using closed-circuit video. The institution actively logs and monitors all communication to the application server (multiple firewall layers prevent direct external communication to the database server) and the system owner is alerted to any unusual activity. If warranted, the institution will immediately as well as automatically ban offending IP addresses at the perimeter before they reach the application server. The application itself also rejects and bans IP addresses of anything it considers abnormal access.

Twilio (<https://www.twilio.com/>) is an IS-Security approved text message platform for research at MUSC and is integrated with REDCap. No data are stored when using Twilio; it only acts as a pass-thru. Personal health information is not sent via text message; only the phone number is used to send the message including a unique link to their web accessible food survey submission.

13.0 Provisions to Monitor the Data to Ensure the Safety of Subjects

DATA AND SAFETY MONITORING PLAN

MUSC has a federal wide assurance for research with human subjects, and is in compliance with federal policy governing use of human subjects. Individuals involved in human subject research at MUSC are required to complete the Collaborative IRB Training Initiative offered online by the University of Miami. All human subject protocols are reviewed through an academic Institutional Review Board (IRB) process that has been accredited by the Association for Accreditation of Human Research Protection Programs. MUSC has an integrated University Compliance Program that is organized via an active compliance liaison and committee structure for financial, clinical, academic and research compliance. This involves universal employee and professional training as well as a confidential Compliance Helpline to encourage all members of the MUSC community to ask questions or voice concerns about topics such as coding and billing, research integrity, professional ethics, human subjects research, animal care and use, biological safety, potential conflicts of interests, patient confidentiality and laws and regulations. Institutional research compliances include a training and certification process for all key personnel engaged in research involving human subjects, vertebrate animals or biohazardous substances, as well as integration into curricula of appropriate instruction in the Responsible Conduct of Research.

Informed consent will be obtained in-person or remotely using MUSC's Teleconsent platform or by telephone. Consent will only be obtained from the participant. Children and cognitively impaired adults will not be enrolled.

If the informed consent is obtained in-person, the consent discussion will take place in a private area and the potential participant will be given the opportunity to read the consent form and ask questions. The participant will be given a signed copy of the consent form.

If the consent is obtained using MUSC's Teleconsent platform using doxy.me, the potential participant will receive a web link which allows study personnel to present the consent form and allows the potential participant to ask questions and read the consent form. The consent form is signed by both parties using this platform and the participant may print a copy for their record.

If the consent is obtained via telephone, the consent form will be sent to the potential participant. Study personnel will speak with the potential participant via a telephone call to discuss the consent form and answer any questions. The participant may then sign the consent form and send the consent form to study personnel. Study personnel will sign the consent form. A signed copy of the consent form will be provided to the participant..

Example 1:

a. Our data and safety and monitoring plan will monitor all patients to ensure the safety of participants and the validity and integrity of the data. Protection to participants will be in accordance with guidelines set forth by NIH. [name] has vast experience in clinical trials and has completed several trials. The level of monitoring will be as rigorous as in the prior published clinical trials. All serious, unexpected, AND related adverse events will be reported to the IRB.

b. Study will be registered in ClinicalTrials.gov before the first subject is enrolled.

Any change in endpoints or analysis plan that occurs will be amended in ClinicalTrials.gov.

The reporting of summary results information (including adverse events) will occur no later than 1 year after the completion date.

Example 2:

All adverse events (AE) will be reported and monitored. The AE's will be characterized by: intensity/severity; expectedness; relatedness; frequency; outcome; treatment or action taken.

Monitoring will be performed at each study visit by the study coordinator and PI, adverse events will also be monitored during regularly scheduled visits (pre-intervention, weekly for first month, alternate weeks for second month and once during last month of study) with the psychologist or dietitian and such events will be reported to PI. All AEs will be recorded on an event form with physician/nurses/coordinator notes attached.

These will be reviewed by [name] and [name].

We will have local study team meetings on a quarterly basis to address the following areas: 1. Review progress of the research study, including participant recruitment, retention and adherence. 2. Review adverse events to determine whether there is any change to anticipated benefit-to-risk ratio of study participation, and whether the study should be continue as originally designed or be changed or terminated. 3. Review data forms, data quality and data confidentiality. Drs. [name] and [name] will arrange for the meetings quarterly, make all materials available for review by the study team and be ultimately responsible for the meetings.

All serious, unexpected, AND related adverse events will be reported to the MUSC IRB within 10 working days of learning of the event.

Overall, the risks involved in this study are truly minimal and therefore based on the potential personal benefit to the enrolled volunteers and the overall knowledge gained, reasonable.

